Influence of Custom Orthosis Post Carpometacarpal (CMC) Arthroplasty

NCT050307510

Document date: document created for submission to UToledo IRB. Approval date of IRB 2/21/22.

THE ELEMENTS OF A RESEARCH PROTOCOL

Influence of custom orthosis post CMC arthroplasty

1. Background, Review of the Literature, Significance

Carpometacarpal (CMC) osteoarthritis (OA) can cause severe pain and loss of hand function, thumb motion and thumb strength (Fontana et al., 2007). CMC arthroplasty, surgery on the thumb joint, is conducted when conservative treatments for CMC OA fail (Grenier et al. 2016). In 2011, 6,960 CMC arthroplasties were conducted in the United States (Werner et al., 2015). Splints or orthoses are typically used after surgery to immobilize the joint as the wound heals. Previous studies have reported mixed results in the comparison of outcomes related to use of custom orthoses and prefabricated splints (Baradaran et al., 2018; Sillem et al., 2011; Marotta et al., 2020; Bani et al., 2013). This study aims to compare post-surgical outcomes, including wound dehiscence, pain, function, and satisfaction with device and care from individuals who receive either a custom orthosis or prefabricated splint after CMC arthroplasty. This study will allow for increased understanding about the pros and cons of prefabricated splints versus custom orthosis which can inform clinical decisions in order to decrease wound dehiscence, the pain associated with wound dehiscence, and enhance function post-surgery for individuals who have CMC arthroplasty.

2. Objectives/Specific Aims

- To determine the difference in the incidence of wound dehiscence after a CMC arthroplasty when using a custom orthosis as compared to a prefabricated splint.
- To determine the difference in subject reported pain levels after a CMC arthroplasty between those who received a custom orthosis as compared to those who received a prefabricated splint.
- To determine the difference in function as measured by the QuickDASH, active range of motion measurements of the thumb, and subtests within the applied dexterity section of the Arthritis Hand Function Test (AHFT) between those wearing a custom orthosis as compared to those wearing a prefabricated splint.
- To determine the difference in subject satisfaction with device and services at the first and second post-operative appointment.

3. Methods

a) **Study Design**

- Experimental, two groups with random assignment

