b) **Method of treatment assignment**

Subjects will be randomly assigned using at the initial follow-up appointment following CMC arthroplasty. The surgeon may exclude the subject, following assessment, if the subject cannot be randomly assigned to an intervention group. Open-label blinding will be used since every member of the team will be able to perceive whether the subject has

received a custom orthosis or prefabricated splint. Random assignment to the two groups will be completed in SPSS.

c) Inclusion/exclusion criteria

Inclusion criteria for subjects include status post CMC arthroplasty (within 4-5 weeks), 18 or older, able to read and understand English, capable of independently consenting to health care procedures.

Subjects will be excluded from the study if the surgeon identifies risk factors that would preclude random assignment to the control or experimental group. Subjects will also be excluded if they request a prefabricated or custom orthosis.

d) Justification of the number of subjects

Anticipated number of subjects that will be requested for enrollment is 125 subjects. A sample size of at least 96 is required for a power of 60 with $\alpha = .05$.

e) Study setting

University of Toledo Medical Center (UTMC) outpatient.

f) Primary and secondary outcome measures

Primary Outcomes include:

Function - as measured by the QuickDASH

Wound dehiscence – as measured by the Sandy Grading System

Pain - as measured by the Visual Analog Pain Scale

Thumb CMC Active Range of Motion (AROM) measurements

Subtests within the applied dexterity section of the Arthritis Hand Function Test

Satisfaction with device and services – as measured by the OPUS.

Secondary variables of interest include:

Demographic data such as age, gender, race, handedness, pre-existing conditions current medications and supplements, smoking history, and alcohol consumption.

h) Procedures, interventions, schedule

FIRST POST-OP APPOINTMENT

Standard of care: At the initial post-op appointment with the surgeon, the client will check in and register for the appointment. A member of the surgical team will assess the client and document the Sandy Score.

Research specific: As a member of the surgical team assesses the client he/she will determine if the client meets the inclusion criteria. If the client does meet the inclusion criteria, the study will be briefly explained using the recruitment flyer. The client will then be asked if he/she is interested in participating.

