If the client is interested in participating, a member of research team will meet with the client to review the consent form and answer any questions. Once any questions have been answered, if the subject agrees to participate, he/she will sign the informed consent form. The subjects will be informed both verbally and in writing that they can take consent away at any

time during the research study. A copy of the informed consent form will be given to the subject. The client will be randomly assigned to intervention A or intervention B.

Standard of Care: The subject will receive either a prefabricated splint (Intervention A) or custom orthosis (Intervention B).

Research specific: The subject will then be asked to complete the demographic questionnaire, QuickDASH, and the Pain VAS. Thumb CMC active range of motion measurements will then be collected (radial and palmar abduction). Participants will also complete subtests within the applied dexterity section of the Arthritis Hand Function Test and OPUS survey.

Subjects who are assigned to Intervention A (the prefabricated splint group) will be provided a splint by a member of the surgical team. Subjects who are assigned to Intervention B (the custom orthosis group) will be evaluated by an occupational therapist and a custom orthosis will be fabricated.

SECOND POST-OP APPOINTMENT

Standard of Care: Approximately 4-5 weeks later, subjects will attend a second post-op appointment and be assessed by a member of the surgical team. The Sandy score will be documented.

Research specific: At this time, a member of the research team will ask the subject to complete the, QuickDASH, and the Pain VAS. Thumb CMC active range of motion measurements will then be collected (radial and palmar abduction). Participants will also complete subtests within the applied dexterity section of the Arthritis Hand Function Test and OPUS survey.

i) Planned data analysis

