Means and standard deviations will be calculated for the demographic information such as age and alcohol consumption per week. In-group and between-group percentages will also be calculated for demographic information, such as gender, pre-existing diabetes, and smoking history. The means and standard deviations of scores received on the QuickDASH, Sandy Grading System, Pain VAS, and AROM will be calculated. In-group and between-group descriptive statistics will be calculated for scores on the OPUS and Applied Dexterity section of the Arthritis Hand Function test. Independent student t-tests will be conducted to compare the means between Interventions A and B. Dependent student t-tests will be conducted to compare the initial post-op assessment mean data to the second post-op assessment mean data within groups. P-values will be considered significant if they are less than or equal to 0.05.

4. Reference List

Baca, M. E., Rozental, T. D., McFarlane, K., Hall, M. J., Ostergaard, P. J., & Harper, C. M. (2020). Trapeziometacarpal joint arthritis: is duration of symptoms a predictor of

surgical outcomes? *The Journal of Hand Surgery*, 45(12), 1184.e1-1184.e7. <https://doi.org/10.1016/j.jhsa.2020.05.026>

Bani, M. A., Arazpour, M., Kashani, R. V., Mousavi, M. E., & Hutchins, S. W. (2013). Comparison of custom-made and prefabricated neoprene splinting in patients with the first carpometacarpal joint osteoarthritis. *Disability & Rehabilitation: Assistive Technology*, 8(3), 232–237. <https://doi.org/10.3109/17483107.2012.699992>

Bani, M. A., Arazpour, M., Kashani, R. V., Mousavi, M. E., Maleki, M., & Hutchins, S. W. (2013). The effect of custom-made splints in patients with the first carpometacarpal joint osteoarthritis. *Prosthetics and Orthotics International*, 37(2), 139–144. <https://doi.org/10.1177/0309364612454047>

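### Aim 1 asks for a difference in incidence of wound dehiscence, but the planned mean Sandy scores and t-tests do not estimate one

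*Combined protocol and SAP*

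**What the plan says.** Section 2 states the first aim: "To determine the difference in the incidence of wound dehiscence after a CMC arthroplasty", custom orthosis against prefabricated splint. Section 3(f) lists dehiscence, graded on the Sandy system, among the primary outcomes.

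Section 3(h) has the score recorded twice. At the first post-operative appointment, "A member of the surgical team will assess the client and document the Sandy Score"; consent and allocation come after that ("The client will be randomly assigned to intervention A or intervention B"). At the second appointment, about 4-5 weeks later, "The Sandy score will be documented".

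Section 3(i) gives the analysis. The Sandy score is treated like the continuous measures: "The means and standard deviations of scores received on the QuickDASH, Sandy Grading System, Pain VAS, and AROM will be calculated". The comparison between arms is: "Independent student t-tests will be conducted to compare the means between Interventions A and B". Within arms, the two visits are compared by dependent t-tests of means. The only percentages are these: "In-group and between-group percentages will also be calculated for demographic information".

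**The concern.** Incidence is a proportion. Section 3(i) plans no count or proportion with dehiscence, no risk difference or ratio, and no test of proportions. The protocol also does not say which Sandy grade, or which visit, defines a case. An analyst who follows the plan exactly will report a difference in mean grade. That figure cannot be converted to an incidence without further information.

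The first aim, on a listed primary outcome, would then go unanswered although the scores are on file. If someone tabulates dehiscence anyway, the threshold and visit would be chosen after the data are seen, in a study that section 3(b) describes as open-label.

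**Working it through.** **Inputs from the documents.** At least 96 subjects (section 3(d)), two groups (section 3(a)), significance at 0.05 (section 3(i)).

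**Assumptions, because the documents do not give them.** Equal allocation (96 / 2 = 48 per arm), two-sided tests, Sandy coding 0 = no dehiscence and 1 to 4 = increasing severity, and all dehiscence rates and severity mixes below.

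**The plan's own figure.** The sample-size sentence ("A sample size of at least 96 is required for a power of 60") names no outcome, effect size, standard deviation or rate, so 96 cannot be reproduced. Reading the power as 60%, it corresponds to a standardised difference of (1.960 + 0.253) × √(2/48) = 0.452. A normal-approximation comparison of 20% with 5% also gives 96. Neither input is in the documents, so 96 is no evidence that the trial was sized for Aim 1. Nothing below depends on it.

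**Step 1: what a mean grade measures.** With 0 for no dehiscence, mean grade = incidence × mean grade among those who dehisce. It equals incidence only if the variable is coded 0/1, and it is proportional to incidence only if severity is the same in both arms. The plan analyses scores and provides no 0/1 coding.

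**Step 2: equal means, different incidence (constructed).** Arm 1 has 12 of 48 at grade 1; arm 2 has 3 of 48 at grade 4.
- Means: 12 × 1 / 48 = 0.25 and 3 × 4 / 48 = 0.25; t-test p = 1.00.
- Incidence: 12/48 = 25.0% and 3/48 = 6.25%; risk difference 0.1875.
- Newcombe 95% interval, from Wilson limits 0.149 to 0.388 and 0.021 to 0.168: lower 0.1875 − √[(0.25 − 0.149)² + (0.168 − 0.0625)²] = 0.041; upper 0.1875 + √[(0.388 − 0.25)² + (0.0625 − 0.021)²] = 0.331.
- Chi-square = 96 × (12 × 45 − 3 × 36)² / (48 × 48 × 15 × 81) = 6.4, p = 0.011; Fisher p = 0.022.

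**Step 3: equal incidence, different means (constructed).** With 8 of 48 in each arm (16.7%), all at grade 1 in one arm and all at grade 4 in the other, the means are 8/48 = 0.17 and 32/48 = 0.67; t-test p = 0.028.

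**Step 4: rejection rates at 48 per arm.** Fisher and uncorrected chi-square are by exact binomial enumeration; the t-test is by 20,000 simulated trials. The same-mix rows use three splits of grades 1 to 4: 25/25/25/25, 60/20/10/10 and 50/30/15/5%. The different-mix rows use 60/20/10/10 in the first arm (mean grade among cases 1.7) and 10/20/30/40 in the second (mean 3.0).

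| Incidence | Severity mix | t-test on grade | Fisher | Chi-square |
|---|---|---|---|---|
| 25% v 6.25% | same | 63-66% | 63% | 76% |
| 20% v 5% | same | 52-55% | 48% | 66% |
| 25% v 6.25% | different | 31% | 63% | 76% |
| 20% v 20% | different | 20% | 3% | 5% |

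In the third row the expected means are 0.25 × 1.7 = 0.425 and 0.0625 × 3.0 = 0.1875, so milder wounds in the arm with more events hide much of the difference. In the fourth they are 0.20 × 1.7 = 0.34 and 0.20 × 3.0 = 0.60: the means differ and the incidences do not.

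**The case against.** The textual mismatch is hard to dispute, but several qualifications are fair.

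- **The divergent cases were built to diverge.** This stands. If nearly all events share one grade, the t-test behaves like a test of proportions: 12 against 3 events, all at grade 1, gives p = 0.011 for both the t-test and chi-square. The cases show what can happen and are not forecasts.
- **Status at the second visit is not strictly incidence.** It includes wounds already open before assignment and misses any that opened and closed between visits. This stands as a limit of two recorded scores. The comparison is still fair, because all randomised subjects are kept and the first score precedes allocation.
- **A yes/no endpoint can cost power.** This stands in part. Using chi-square, with Fisher when an expected count is below 5, power is 75.6% at 25% v 6.25% and 61.5% at 20% v 5%, above the same-mix t-test. At 10% v 5% it is 8.4%, against 11-12% for the t-test. Neither is useful there.
- **A threshold may be set out in the cited wound-grading sources.** Possibly, but the protocol does not adopt one. Even with a threshold, section 3(i) would still plan no proportion.
- **The repair is only a short paragraph.** True, but that bears on its cost and not on whether it is needed.

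**Conclusion.** The concern holds and should be corrected before analysis. The analysis as written estimates a difference in mean grade, whereas Aim 1 asks for a difference in incidence. That conclusion comes from the text alone and needs none of the assumed rates.

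The main loss is the missing estimate. When severity is similar in both arms, the t-test has about the power of Fisher's test and less than chi-square at the two larger differences examined. When severity differs, the t-test can depart from incidence in either direction: in the assumed scenarios its power falls to 31% where Fisher has 63%, and it rejects in about 20% of trials where incidence is equal. Those sizes rest on 48 per arm, 0-4 coding and the stated rates and mixes.

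**What to change.** For Aim 1, replace the t-test on the Sandy score in section 3(i) with a comparison of proportions, specified before analysis:

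- State which Sandy grade counts as dehiscence. This is the investigators' choice.
- Report n/N with dehiscence at the second visit by arm, in all randomised subjects as assigned. Give the number without a second-visit score and say in advance how they enter N.
- Give the risk difference with a 95% confidence interval and one pre-named test or rule, for example chi-square, or Fisher's exact test if an expected count is below 5.
- Report first-visit dehiscence by arm as a baseline characteristic, since it is scored before assignment. New dehiscence among subjects free of it at that visit can be a supporting analysis.
- Keep severity as a secondary ordinal or descriptive summary.

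**Cost.** No new data are needed for status at each visit, as both scores are already documented; they cannot capture dehiscence that came and went between visits. The yes/no endpoint discards severity and may have low power: at 48 per arm, Fisher / chi-square power is 18% / 29% for an assumed 20% v 10%, and 6% / 17% for 10% v 5%. The sample-size sentence should not be read as powering this comparison and should be revisited.

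### Section 3.i names neither a visit nor a covariate for the between-arm t-tests; a baseline-adjusted second-visit comparison would be more precise, but only if the baseline is scored before assignment is revealed

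*Combined protocol and SAP*

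**What the plan says.** Section 3.i (Planned data analysis) has two sentences on testing. Between arms: "Independent student t-tests will be conducted to compare the means between Interventions A and B". Within arms: "Dependent student t-tests will be conducted to compare the initial post-op assessment mean data to the second post-op assessment mean data within groups". The first names no visit, covariate or change score. For two instruments the section adds: "In-group and between-group descriptive statistics will be calculated for scores on the OPUS and Applied Dexterity section of the Arthritis Hand Function test". It does not say whether the t-tests extend to them.

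Section 3.h (Procedures) has QuickDASH, pain VAS, thumb AROM, AHFT and OPUS recorded at both post-operative appointments, and the Sandy grade documented at both. At the first appointment the order is:

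- Before eligibility and consent: "A member of the surgical team will assess the client and document the Sandy Score".
- After consent: "The client will be randomly assigned to intervention A or intervention B". The next paragraph says that the subject gets one device or the other.
- After that: "The subject will then be asked to complete the demographic questionnaire, QuickDASH, and the Pain VAS". AROM, AHFT and OPUS follow.
- In a later paragraph, device provision is described again, for example "Subjects who are assigned to Intervention A (the prefabricated splint group) will be provided a splint by a member of the surgical team".

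Section 3.b makes the trial open-label. Section 3.d plans to approach 125 subjects and gives a minimum of 96 for a power figure of 60 at alpha 0.05.

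**The concern.** The first three aims in section 2 are contrasts between devices, and paired tests within each arm answer none of them. The between-arm sentence is therefore the whole of the comparative analysis, and it leaves open which visit is compared and whether a subject's own starting score is taken into account.

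With stated power of only 60, precision is worth recovering, and the trial already collects the scores needed. The obvious remedy, regressing the second-visit score on arm and first-visit score, has a catch. In an open-label trial, a score taken after the subject knows the assignment, and perhaps after the device is on, may already carry a device effect. Adjusting for it would then move the estimate. The first-visit Sandy grade is the exception, because it is documented before assignment.

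**Working it through.** **Inputs from the documents.** N=96, power 60 and alpha 0.05 (section 3.d); 125 subjects to be approached (section 3.d); two randomised groups (section 3.a).

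**Assumptions not in the documents.** Power 60 means 60%; 96 is the total, split 48 and 48; the test is two-sided; r is the correlation between a subject's first- and second-visit scores, taken over a range.

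**Step 1: the plan's own figure.** The 96 cannot be reproduced, because section 3.d states no endpoint, test or effect size. It can only be back-solved. For a two-sample t-test with n per arm, the noncentrality is d × √(n/2) with 2n − 2 degrees of freedom. With n=48 (94 df), 60% power needs d = 0.4565. The normal approximation agrees: (1.960 + 0.253)/√24 = 0.452. With the same d and all 125 analysed (62 and 63, 123 df), unadjusted power is 71.6%.

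**Step 2: gain from a true baseline.** Regression on arm and baseline multiplies the residual SD by √(1 − r²), so the effective difference is d/√(1 − r²) on N − 3 df. Example, r=0.5: 0.4565/0.866 = 0.527, giving 72.4% at N=96. The formula ignores chance imbalance at the first visit, so simulated power (60,000 trials per cell) is shown beside it.

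| r | N=96, formula | N=96, simulated | CI width relative to unadjusted | N=125, simulated |
|---|---|---|---|---|
| 0 | – | 59.5% | 1.005 | 71.5% |
| 0.1 | – | 59.9% | 1.000 | 71.5% |
| 0.2 | 61.7% | 61.2% | 0.985 | 73.3% |
| 0.3 | 64.1% | 63.4% | 0.959 | 75.1% |
| 0.4 | 67.5% | 66.9% | 0.922 | 78.6% |
| 0.5 | 72.4% | 72.4% | 0.871 | 83.0% |
| 0.6 | 79.0% | 78.8% | 0.805 | 88.3% |

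The comparators are 60% at N=96 and 71.6% at N=125. At r=0.2 the gain at N=96 is about one point; at 0.1 or below there is none.

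**Step 3: what happens if the first-visit score is not a true baseline.** If the device has already shifted that score by e SD, the expected adjusted estimate is d − r × e. With r=0.5 and e=+0.2: 0.456 − 0.5 × 0.2 = 0.356. With e=−0.2: 0.556. With no true second-visit difference and e=0.2, the simulated rejection rate at N=96 is 6.3% (r=0.3) or 8.6% (r=0.5) instead of 5%. The power gain is cancelled when (d − r × e)/√(1 − r²) = d, that is e = d(1 − √(1 − r²))/r. This gives 0.456 × 0.046/0.3 = 0.07 SD at r=0.3 and 0.456 × 0.134/0.5 = 0.12 SD at r=0.5. Timing therefore has to be settled before adjustment is adopted.

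**The case against.** The strongest reply is that a second-visit t-test is valid and adjustment is only an efficiency preference. Its gain rests on an r that the documents do not give and on a d back-solved from a sample size whose endpoint is unstated. That stands, and it limits the point to precision.

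Secondly, section 3.h can be read as device first, scores second, with the later paragraph saying only who supplies each device. First-visit OPUS, which covers satisfaction with the device, fits that order. On this reading the scores are post-device and, without a change of procedure, the right analysis is the unadjusted one. That also stands, and the fix allows for it.

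A reader might go further in three ways that the text does not support:

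- That first-visit scores are unused between arms. With no visit named, this cannot be established; a t-test at each visit is an open reading.
- That the shifted estimates and raised rejection rates in Step 3 are faults of the plan. The plan adjusts for nothing, so they are hazards of a careless remedy.
- That the within-arm p-values will be used to compare devices. Section 3.i gives those tests a within-group purpose and says nothing of the kind.

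**Conclusion.** The point holds as a matter of precision. Section 3.i leaves the visit and any covariate unstated, and the better analysis is a second-visit comparison adjusted for a score taken before assignment is revealed. Under 1:1 allocation, a two-sided test and d = 0.456, the gain at N=96 is from 60% to between 61% and 79% power for r from 0.2 to 0.6, with confidence intervals about 1.5% to 19.5% narrower. It is negligible at r of 0.2 or below. Nothing in the documents shows where r lies for any of these scores.

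The planned t-test at the second visit is not biased. As section 3.h stands, only the first-visit Sandy grade is clearly a pre-assignment measurement. A between-arm test of that grade could not answer the first aim, though nothing says that one is intended.

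**What to change.** 1. In section 3.h, reconcile the two descriptions of device provision. Have first-visit QuickDASH and pain VAS completed after consent and before assignment is revealed, and AROM and AHFT too if the surgical team agrees that they can be tested then. OPUS stays after the device.
2. In section 3.i, name the second visit as the main between-arm comparison. For each measure collected before assignment, use linear regression of the second-visit value on arm and first-visit value, reported as an adjusted difference with a 95% confidence interval. For any measure not so collected, keep the unadjusted second-visit comparison. Fix the choice for each measure before outcome data are examined.
3. The first-visit Sandy grade may serve as a baseline; do not test it between arms as an outcome.

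Cost: naming the visit takes one phrase. The regression uses one degree of freedom per model and can be run in SPSS, which section 3.b already uses for the random assignment. Moving the measures is a small re-ordering of the first visit through an IRB amendment. It also gives up any first-visit comparison of those measures in the device, which the third aim may intend, since it speaks of subjects wearing one.

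### Six unranked primary outcomes, t-tested between arms at 0.05 each, with no outcome, visit, adjustment or success rule to say which comparison decides the device question

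*Combined protocol and SAP*

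**What the plan says.** Section 3.f opens with "Primary Outcomes include" and lists six items with no order among them: QuickDASH, the Sandy wound grade, pain VAS, thumb AROM, the AHFT applied dexterity subtests and OPUS. Section 3.h collects all six at both post-operative appointments, with AROM recorded as two movements.

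Section 3.i treats the six in two groups. For four of them: "The means and standard deviations of scores received on the QuickDASH, Sandy Grading System, Pain VAS, and AROM will be calculated". For the other two: "In-group and between-group descriptive statistics will be calculated for scores on the OPUS and Applied Dexterity section of the Arthritis Hand Function test". It then says "Independent student t-tests will be conducted to compare the means between Interventions A and B", naming neither outcome nor visit, and adds paired tests between visits within each arm. The decision rule for every test is "P-values will be considered significant if they are less than or equal to 0.05".

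Section 2 has four aims: dehiscence, pain, function and satisfaction. Aim 3 (function) covers three measures, including "subtests within the applied dexterity section of the Arthritis Hand Function Test (AHFT) between those wearing a custom orthosis as compared to" those in a prefabricated splint. Aim 4 reads "To determine the difference in subject satisfaction with device and services at the first and second post-operative appointment".

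Section 3.d gives at least 96 subjects, power of 60 and one alpha of .05, without naming an outcome.

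**The concern.** A two-arm trial controls its false-positive risk at 5% only if it is fixed in advance which comparison decides the question, or if the level is shared among several. This plan does neither. It offers several between-arm comparisons, each at the full 0.05, and says nothing about which carries the conclusion or how disagreement among them is to be read.

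At stake is a statement that custom and prefabricated devices differ when they do not. All six outcomes are named in advance, so the risk is not that new outcomes appear. It is that the outcome or visit treated as decisive can be picked once the results are known.

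**Working it through.** **Step 1: the plan's own figure.** Section 3.d states N = 96, power 60 (read as 60%) and alpha .05, with no effect size, SD or event rate, so 96 can be neither confirmed nor refuted. Assuming 48 per arm, two-sided testing and a continuous outcome, the implied standardised difference is d = (1.960 + 0.253)/√(48/2) = 0.452 by the normal approximation, or 0.456 with the t distribution. It is used only to illustrate power in step 6.

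**Step 2: how many between-arm tests?** Section 3.i computes means for four primaries, and its t-test sentence compares means, so four is a reasonable reading. It is an inference: 3.i also computes means for age and alcohol consumption. OPUS and AHFT appear only under descriptive statistics, yet aims 3 and 4 ask for differences on them. So k = 4, or up to 6.

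**Step 3: any one significant primary at one visit.** Assumptions: no true difference on any outcome, two-sided 0.05 (sidedness is not stated), one test per outcome.

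- Independent tests: 1 − 0.95^k.
- Equal pairwise correlation r between normal test statistics, c = 1.96: 1 − ∫ φ(u) [Φ((c − √r·u)/√(1−r)) − Φ((−c − √r·u)/√(1−r))]^k du.

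| k | r = 0 | 0.3 | 0.5 | 0.7 | 0.9 |
|---|---|---|---|---|---|
| 4 | 18.5% | 17.4% | 15.6% | 13.0% | 9.4% |
| 6 | 26.5% | 24.1% | 20.7% | 16.4% | 10.8% |

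**Step 4: what moves these figures at one visit.**

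- Testing the two AROM movements separately gives k = 5 or 7: 1 − 0.95^5 = 22.6% and 1 − 0.95^7 = 30.2% if independent; 10.2% and 11.4% at r = 0.9. The number of AHFT subtests is not given, so no figure is possible for splitting them.
- A sparse Sandy score makes its t-test conservative. Treated as a 0/1 outcome at an assumed 2% incidence with 48 per arm, the test's exact size is 1.2%. The independent rates become 1 − 0.9882 × 0.95³ = 15.3% (k = 4) and 1 − 0.9882 × 0.95⁵ = 23.5% (k = 6).

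**Step 5: the aims as separate questions, 5% each.**

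- Aims 1 and 2 have one instrument each: 5% at one visit, no inflation.
- Aim 3 has QuickDASH, AROM and AHFT. Three tests: 1 − 0.95³ = 14.3% independent, 8.4% at r = 0.9. If AHFT is descriptive only, two tests: 1 − 0.95² = 9.75% independent, 7.0% at r = 0.9.
- Aim 4 has one instrument but names two visits.

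**Both visits.** First-visit Sandy is recorded when the surgical team assesses the client, before consent and random assignment (section 3.h). It cannot be a device comparison. With one test per outcome, both visits therefore give at most 4 + 3 = 7 or 6 + 5 = 11 tests. Eleven independent tests give 1 − 0.95^11 = 43.1%, an upper illustration, because the same measure on the same patient 4–5 weeks apart will be correlated. Within-group paired tests do not compare devices and are not counted.

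**Step 6: the price of adjustment.** Holm rejects at least whatever Bonferroni rejects, so power at 0.05/k is the guaranteed per-outcome power. With d = 0.456 (noncentral t):

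| Level | N = 96 | N = 125, all analysed |
|---|---|---|
| 0.05 (one primary) | 60% | 72% |
| 0.05/4 | 38% | 51% |
| 0.05/6 | 33% | 45% |
| 0.05/7 | 31% | 43% |

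**The case against.** The strongest reply is that the plan nowhere says that one significant result settles the matter. Section 2 sets out four aims, and section 1 speaks of weighing the pros and cons of each device rather than reaching a single verdict. On that reading aims 1 and 2 run at 5% each and need no adjustment. This stands, and it is why the any-win percentages are conditional. It does not clear the plan: the separate-aims rule is not stated either, aim 3 holds two or three tested measures with no rule for combining them, and aim 4 names two visits.

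A second reply is that the second visit is the natural comparison. The other first-visit measures come at the same appointment as assignment, with little time in the device, and 3.i uses that visit as the starting value for the paired tests. This is fair for aims 1 to 3, but the plan does not say it.

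A reader might infer that this trial carries a 26.5% false-positive risk, or more than 40% over two visits. The documents do not support that. Those figures need an any-win rule that the plan does not contain and independence that the documents give no basis for; the two-visit figure also needs every eligible first-visit test to count. Nor can one say that four outcomes are certainly t-tested, since the t-test sentence names none.

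**Conclusion.** The concern holds as a gap in the decision rule. Six unranked primaries, unspecified between-arm t-tests and a flat 0.05 leave open which comparison answers the device question. That much is read directly from sections 3.f and 3.i.

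The size is illustrative. It depends on the number of tests, the correlation and the rule finally used: roughly 9% to 26.5% at one visit if any one of four to six primaries counts, with AROM splitting pushing it up and a sparse Sandy score pulling it down. If the aims are separate questions, the excess lies mainly in aim 3 (about 7% to 14%) and in aim 4's two visits. On either reading the plan does not hold every device question at 5%. The choice is credible only if made before the outcome data are examined.

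**What to change.** **Preferred.** In 3.f, name one primary score at the second visit, tested between arms at 0.05, and make the other outcomes secondary. In 3.i, state that a device difference is claimed only on that primary, and label the first-visit and within-group tests supportive or descriptive.

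**If several primaries are kept.** Pre-name one score for each (none is defined for AROM, AHFT or OPUS) and apply Holm at overall 0.05 across the second-visit between-arm comparisons. Add first-visit OPUS to that family unless aim 4 is reworded.

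**If the aims are meant as separate questions at 5% each.** Say so, name one deciding measure for aim 3 and one deciding visit per aim, and make no overall device claim from a single aim.

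**In all cases.** State in 3.i whether OPUS and AHFT are t-tested, and in 3.d which outcome and alpha the 96 subjects and 60% power refer to.

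**Cost.** Wording in 3.d, 3.f and 3.i, and possibly aim 4; no new data. Fewer results can be called significant, and the sponsor must commit in advance. A single primary keeps the full 0.05, so it loses no power on that outcome. Holm has the lower guaranteed per-outcome power shown in step 6.
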